### 3 Synopsis

Sponsor: Lyndra Inc.	Investigational Medicinal Product: Memantine Hydrochloride Modified Release Prototype Capsule	EudraCT No.: 2017-000982-61
Title of Study:		
A Study Designed to Determine the Gastro-Retentive and Modified Release Properties of Memantine Hydrochloride Prototype Capsule Formulations in Healthy Subjects		
Principal Investigator:		
[name] MBChB, MRCS (Ed)		
Study Centre:		
Quotient Clinical, [name]		
Objectives:		
Primary:		

 
To assess the gastro-retentive (GR) properties of memantine hydrochloride modified release (MR) prototype capsules as determined by magnetic resonance imaging (MRI).
 
		
Secondary:		

 
To determine the pharmacokinetics (PK) of memantine hydrochloride when administered as the MR prototype capsules.
 
To provide additional safety and tolerability information for memantine hydrochloride MR prototype capsules.
 
To assess the impact of dosing in the fed state on the PK properties of a selected memantine hydrochloride MR prototype capsule (optional).
 
To assess the impact of dosing in the fed state on the GR properties of a selected memantine hydrochloride MR prototype capsule (optional).
 
		
Exploratory:		

 
To assess the impact of diurnal differences and food consumption on the PK of memantine hydrochloride MR prototype capsule(s) on Days 3 and/or 5 of selected regimen(s).
 
To use abdominal X-ray to confirm the elimination of the elastomeric core of the memantine hydrochloride MR prototype formulations from the body by Day 21 where the formulation contains radiopacifier.
 
		
Methodology:		
This is a single centre, open-label, single dose, 5-period study in 24 healthy male and female subjects, with an optional Period 6, if required. It is expected the study will be executed in 3 cohorts of 8 subjects, with each cohort participating in up to 2 study periods (total of up to 6 study periods). Cohort 3 may be conducted in parallel with Cohort 2.		
Subjects will be dosed in a sequential manner, as appropriate. Each subject will be administered up to 2 regimens across 2 study periods as follows:		

Cohort	Regimen	Investigational Medicinal Product Dose
1	A	50 mg Memantine Hydrochloride MR Prototype Capsule as Formulation 1
	B	50 mg Memantine Hydrochloride MR Prototype Capsule as Formulation 2
2	C	50 mg Memantine Hydrochloride MR Prototype Capsule as Formulation 3
	D	50 mg Memantine Hydrochloride MR Prototype Capsule as Formulation 4
3	E	50 mg Memantine Hydrochloride MR Prototype Capsule as Formulation 5 or a previously dosed MR Prototype Capsule
	F (optional) a	50 mg Memantine Hydrochloride MR Prototype Capsule as Formulation 6 or a previously dosed MR Prototype Capsule

MR, modified release

a Regimen F will be administered to Cohort 3 in Period 2, if required, either in the fasted state or after a breakfast (meal composition to be confirmed [tbc])

Regimens A to E: planned dose administration will be in the fasted state following an overnight (minimum 10 h) fast; however, food status for Regimens B to E may be changed (e.g., administered with a meal composition [tbc]) based on emerging GR properties and PK data from previous regimens

Details of the IMP are provided in the IMP section

There will be a minimum 35-day interval between each dose administration. If at Day 14 of Period 1 plasma PK levels are >20 ng/mL, subjects will not progress to a second treatment period.

An interim decision will take place after each regimen to decide on the memantine hydrochloride MR prototype capsule to dose in the next regimen, prandial status and food composition for dose administration in the subsequent period, and after Regimen E to decide if Regimen F is required. Selection of the MR prototype capsule formulations will only be made after a complete review of all data collected from the previous cohort(s). For selection to occur, data must be available from a minimum of 6 subjects in each regimen who have completed the planned safety, PK and MRI assessments up to 312 h (Day 14). Where the desired GR properties have not been achieved for any dosed formulation the dose decision can select any previously tested formulation to dose again in the fed state during the next study period since it is known that dosing in the fed state can improve gastroretention of oral dosage forms. For all regimens, blood samples will be collected for PK analysis up to Day 35 and there will be the option to increase the number of PK samples over a 24-hour period on Days 3 and/or 5 to assess the impact of diurnal differences and food consumption during the regimen on the PK profile (details provided in [PK Assessments](#) section).

### Study Design:

Subjects will be screened for inclusion in the study in the 28 days before dosing. Each period will follow the same study design. Subjects will be admitted to the clinical unit in the evening prior to product administration (Day -1). It is planned that subjects will be dosed in the morning of Day 1, in a standing position, following an overnight fast (minimum of 10 h) or after a breakfast (light, medium or high fat breakfast to be confirmed) for optional Regimen F. However, the food status for Regimens B to E may be changed (e.g., administered with a meal composition to be confirmed) based on emerging GR properties and PK data from the previous regimens.

There will be an appropriate interval between dosing of subjects based on logistics. In Cohort 1, sentinel dosing of Regimen A will be performed for the first subject, who will be dosed 7 days prior to the remaining 7 subjects in the cohort. The decision to progress with dosing of the remaining subjects in the cohort will be decided by the investigator or delegate and the sponsor's medical monitor based on the available safety data and MRI images up to Day 6.

Subjects will remain in the clinical unit until 168 h post-dose (Day 8) and will return on Days 10, 14, 21, 28 and 35 for PK blood sample collection. MRI scans (at the University of

Nottingham, to assess the GR properties of the capsule formulations) will be performed as described below. X-ray imaging (at Woodthorpe Hospital, to confirm elimination of the elastomeric core from the body by Day 21) may be performed, as described below.

Faecal samples may be collected until 168 h post-dose in order to retrieve the formulation components (2 drug polymer arms, 4 inactive polymer arms and elastomeric core). If faecal analysis shows all formulation components have been retrieved, no further MRI imaging or faecal sample collections will be performed (see below).

Follow-up procedures will take place on Day 35 post-final dose to ensure the ongoing wellbeing of the subjects.

#### MRI scans

Subjects will have an MRI scan performed on Days 2, 4, 7, 10 and 14 of each period to assess the GR properties of the capsule formulations. During periods of residency in the clinic, subjects will be given a light snack the evening before the scheduled MRI scan. During the outpatient phase of the study, subjects will be asked to fast from approximately 23:00 prior to attending the clinic.

After the overnight fast, subjects will receive 50.4 g of carbohydrate as a drink (2 x 200 mL drinks) at least 2 h before the MRI procedure in order to reduce the increased gastric motility resulting from prolonged periods of fasting (in the clinic on Days 2, 4 and 7, and at home on Days 10 and 14), and will then drink at least 500 mL of potable water immediately before the MRI scan. If the MRI confirms that the MR prototype formulation is not resident in the stomach, additional MRI images of the small intestine may be performed on that day to confirm its location. No further MRI scans will be performed on subsequent days if stomach residency is not confirmed.

If complete gastric emptying (all stellate components) is not confirmed on Day 14, subjects will be asked to return for a follow-up MRI scan between Day 14 and Day 25 (allowing a minimum 10-day window before admission to Period 2) to confirm complete gastric emptying of the stellate components. If any MR prototype is still present at this follow-up MRI scan, subjects will not progress to Period 2 and will be managed in accordance with best clinical practice.

#### X-Rays

The elastomeric core will be identifiable for some of the formulations tested and can be detected by X-ray. Where a radiopaque formulation is being tested, 2 abdominal X-ray per subject may be performed during the study (1 per treatment period) in the non-fasted state to to confirm elimination from the body by Day 21.

#### **Number of Subjects Planned:**

A total of 24 healthy male and female (women of non-childbearing potential [WONCBP]) subjects are planned to ensure a minimum of 6 evaluable subjects per regimen. Subjects withdrawn or discontinuing the study prematurely because of an investigational medicinal product (IMP)-related AE or termination of the study will be considered to have completed the study and will not be replaced. Subjects withdrawing for other reasons may be replaced at the discretion of the investigator and sponsor. Up to 4 replacement subjects may be dosed in each cohort to ensure 6 evaluable subjects per regimen.

Subjects will not be allowed to progress to Period 2, but may be replaced if:

- Their plasma level on Day 14 is >20 ng/mL  
Or
- MRI scans show complete gastric emptying (all stellate components) has not occurred by Period 1, Day 25 (see [Study Design](#) section).

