#### **MRI and X-Ray Assessments:**

Analysis of MRI data will be performed on Days 2, 4, 7, 10 and 14 to inform if the stellate formulation is retained in the stomach. If complete gastric emptying (all stellate components) is not confirmed on Day 14, subjects will be asked to return for a follow-up MRI scan between Day 14 and Day 25 (allowing a minimum 10-day window before admission to Period 2) to confirm complete gastric emptying of the stellate components. If any MR prototype is still present in the stomach at this follow-up MRI scan, subjects will not progress to Period 2 and will be managed in accordance with best clinical practice.

X-ray imaging (up to 2 abdominal X-ray per subject during the study; 1 per treatment period) may be performed in the non-fasted state to confirm elimination of the elastomeric core of the memantine hydrochloride MR prototype formulation by Day 21.

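### For the device itself, Period 2 entry requires only an empty stomach by Day 25; the one X-ray that could show a retained core has no bearing on re-dosing

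*Combined protocol and SAP*

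**What the plan says.** All references are to the protocol synopsis, the only part available for this review.

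- **Bars to Period 2** (Number of Subjects Planned): "Subjects will not be allowed to progress to Period 2, but may be replaced if" the Day 14 plasma level exceeds 20 ng/mL, or "MRI scans show complete gastric emptying (all stellate components) has not occurred by Period 1, Day 25". Methodology adds a minimum of 35 days between doses.
- **Follow-up MRI** (MRI scans; MRI and X-Ray Assessments): a subject not confirmed empty on Day 14 returns for one further scan by Day 25, which leaves at least 10 days before Period 2 admission. The second of these sections states the consequence as "If any MR prototype is still present in the stomach at this follow-up MRI scan, subjects will not progress to Period 2".
- **X-ray** (X-Rays): for radiopaque formulations, "2 abdominal X-ray per subject may be performed during the study (1 per treatment period) in the non-fasted state". The related exploratory objective is to confirm that the elastomeric core has gone "from the body by Day 21 where the formulation contains radiopacifier". The synopsis states no action if the film shows the core.
- **Other looks below the stomach:** when the stomach is found empty, "additional MRI images of the small intestine may be performed on that day to confirm its location", and then "No further MRI scans will be performed on subsequent days if stomach residency is not confirmed". Faecal retrieval of components is optional and ends at 168 h (Study Design).

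**The concern.** The plan treats leaving the stomach and leaving the body as separate questions, and only the first governs re-dosing. The dates also do not fit together. A device may stay in the stomach past Day 21 and the subject still qualifies if a scan by Day 25 shows the stomach empty. Yet any device in the stomach on Day 21 has already missed the plan's own elimination target, and the limit of one film per period leaves no planned X-ray to show that it left later.

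At stake is the safety of healthy volunteers. Those who keep the first device longest, or whose film shows a core lower in the gut, are the people in whom clearance most needs checking before a second six-arm device is given. As written, they may be given it.

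**Working it through.** **1. Reproduce the plan's window.** Dose on Day 1 plus the 35-day minimum gives an earliest second dose on Period 1 Day 36. Admission is the evening before, Day 35. From the latest follow-up MRI, 35 − 25 = 10 days, which matches the stated window.

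**2. Place the X-ray on the same scale.** Day 21 is a target for elimination, not a fixed visit. A clear film taken later could not show clearance by that date, so the objective pulls the film to Day 21 or earlier. Taking Day 21:
- to the last acceptable gastric exit: 25 − 21 = 4 days, so follow-up MRIs on Days 22, 23, 24 and 25 come after the film;
- to the earliest second dose: 36 − 21 = 15 days.

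An earlier film widens both gaps.

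**3. Apply the written rules** to subjects given a radiopaque formulation who pass the plasma bar and the 35-day interval.

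| Period 1 findings | Stomach criterion | Film | Progresses as written? |
|---|---|---|---|
| Empty by Day 14, no core on film | Met | Clear | Yes, core shown to have gone |
| Empty by Day 14, core visible on film | Met | Not clear | Yes |
| In stomach at film (by Day 21), follow-up MRI on Days 22 to 25 shows empty | Met | Not clear, none left | Yes |
| Still in stomach at the follow-up MRI | Failed | Any | No |

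Rows two and three are the gap.

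**4. Do the other checks close it?** Faecal retrieval ends at 168 h, which is Day 168/24 + 1 = Day 8. That is 36 − 8 = 28 days before the earliest second dose, and too early for any device still in the stomach on Day 14. Small-intestine MRI is optional and tied to the day the stomach is found empty. It can locate a device, but no later scan is planned to show that it left. Neither is listed as a progression criterion.

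**5. How many second doses pass through this rule?** Cohorts 1 and 2: 2 × 8 = 16. With Regimen F: 3 × 8 = 24. This is the number the rule governs, before replacements and drop-outs, and not the number affected. The gastric exit times needed to estimate the latter are not in the documents.

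**The case against.** The strongest reply is that the design already deals with this by time. The 10-day window is deliberate, and the Investigational Medicinal Product section says the disintegrating matrices are meant to control gastric exit and protect the gut. A device that has left the stomach by Day 25 has probably left the body by Day 35. That stands, and it keeps the safety concern modest. But the window is an allowance, not a check; no intestinal transit time is given; and the plan's own film may show that the allowance has not yet sufficed.

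A reader might also draw stronger conclusions that the documents do not support:

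- **That an empty stomach is the only condition for Period 2.** The plasma bar and the 35-day interval also apply.
- **That a given number of subjects will be re-dosed with a device inside them.** Only one follow-up MRI is planned, and anyone still retained at that scan is barred. Late exit therefore leads to re-dosing only when the scan falls after the exit. Any count would rest on an exit rate that the documents do not supply.
- **That Period 2 data would be misread.** Period 2 Day 21 is Period 1 Day 35 + 21 = 56, so a confusing film needs a core still present 56 − 25 = 31 days after the latest accepted exit. Contaminated faecal retrieval needs parts to stay at least 36 − 25 = 11 days, optional collection to be in use, and those parts to complete a set. Both are remote.
- **That the MRI rule contradicts itself.** The MRI scans section says "If any MR prototype is still present at this follow-up MRI scan, subjects will not progress to Period 2", without naming the stomach. The preceding sentence is about confirming gastric emptying, so the meaning is the same as elsewhere. Aligning the wording is editorial.

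Finally, an investigator who saw a core on film might well withhold the second dose, and later protocol sections may say so. Neither can be confirmed from the synopsis.

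**Conclusion.** The point holds as a gap in a stated safety rule. Two kinds of subject may receive a second device with the first not shown to have left the body: those with an empty stomach and a core visible on film, and those whose stomach empties on Days 22 to 25 after the film. The second route assumes the film is taken on or before Day 21, as the objective implies.

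The gap covers up to 15 days before the earliest second dose, on a rule governing 16 second doses (24 with Regimen F). The probability of harm cannot be estimated from the documents and is probably low because of the 10-day window. The case for change is that the repair uses a film already planned. The conclusion applies to the synopsis only. It says nothing of non-radiopaque formulations beyond the fact that an empty stomach and the window are all they have, apart from the optional checks in step 4.

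**What to change.** Make two changes, both for radiopaque formulations.

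1. **Add a third bullet under Number of Subjects Planned:** no progression to Period 2 if the last Period 1 X-ray shows the elastomeric core. The subject may be replaced, as for the other two bullets.
2. **Re-time the film in late emptiers:** where gastric emptying is not confirmed by Day 21, take that period's single X-ray after the MRI that confirms emptying, at the existing Day 28 or Day 35 visit. The site will know on Day 21 whether emptying has been confirmed, so it can hold the film then.

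Day 28 leaves 35 − 28 = 7 days before the earliest admission to act on the result. Day 35 allows the longest transit, but the film must be read before the second dose.

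**Cost.** No X-ray is added, and the cap of one per period stays. The few late emptiers lose the exploratory reading at Day 21, because an empty stomach on Days 22 to 25 cannot show whether the core had gone by then. A subject whose only film shows the core is barred even if it would have passed before Day 36, and on Day 28 or Day 35 that loss comes late. Each cohort of 8 can lose 8 − 6 = 2 before falling below the minimum of 6 evaluable subjects per regimen, and up to 4 replacements per cohort are already allowed.

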**Duration of Study:**

Single dose administration on up to 2 occasions in 3 separate cohorts of subjects (Cohorts 1, 2 and 3).

The estimated time from screening to the end of the study for each subject is approximately 14 weeks.

**Main Inclusion Criteria:**

- Healthy male and female (WONCBP only) subjects aged 18 to 60 years.
- Body mass index 18.0 to 32.0 kg/m^2 or, if outside the range, considered not clinically significant by the investigator.
- Male subjects must agree to the use of an adequate method of contraception for up to 35 days post-dose. No methods of contraception are required for female (WONCBP) subjects.
- Willingness to undergo serial MRI scans and abdominal X-rays.
- Subject is aware of the specific risks around MRI scans (including claustrophobia and rarely, tingling or burning at tattoo sites).
- Subject must agree to remove all piercings prior to MRI imaging.
- Subjects must demonstrate their ability to swallow a size 000 empty white opaque capsule at screening.
- Must agree not to drive or to operate heavy machinery for up to 17 days post dose (Day 18) due to possible adverse effects of memantine (e.g., somnolence, dizziness, confusion, hallucinations, balance disorders etc).
- Subject must have a negative screening faecal occult blood test

**Investigational Medicinal Product, Dose and Mode of Administration:**

The IMP, memantine hydrochloride MR prototype capsule (50 mg) will be used in this study, and will be administered as Memantine Hydrochloride MR Prototype Capsule Formulations 1 to 6.

The intermediate formulation consists of 4 primary components; an elastomeric core (which ensures deployment of the dosage form), 2 drug polymer arms (which contain and release the drug), 4 inactive polymer arms (which maintain the structural integrity of the stellate formulation), and 6 disintegrating matrices on the arms (which are intended to control gastric exit and gastrointestinal safety). The intermediate formulation is encapsulated into a Size 00 EL capsule. Once the capsule dissolves in the stomach, the formulation opens to form a 6-arm stellate structure. The elastomeric core can also incorporate a radiopacifier so that the location can be identified by X-ray after oral administration.

Administration will be by the oral route. The memantine hydrochloride MR prototype capsules will be administered with a total of 340 mL of water (consisting of 40 mL given immediately prior to dosing and 200 mL given with the IMP) while subjects are standing. A further 100 mL of water (bolus wash) will be given immediately after dosing. Each volume of water given will be swallowed in one go and will not be sipped.

**Pharmacokinetic Assessments:**

Venous blood samples for PK analysis will be collected at regular time intervals.

Up to an additional 10 PK samples may be taken over a 24-h period on Days 3 and/or 5 if the option is taken to assess the impact of diurnal differences and food consumption during the regimen on the PK profile (see [Study Design](#) section). During Regimen A of Cohort 1, these additional samples will be collected at 4-h intervals throughout Days 3 and/or 5. In subsequent cohorts and/or regimens, this schedule may be adjusted based on emerging PK data from previous regimens, subject to the restriction that up to 10 additional samples may be taken in total over a 24-h period on Days 3 and/or 5 for this purpose. If the MRI imaging on Days 2

and/or 4 shows that the MR prototype formulation is no longer resident in the stomach, the additional PK sampling will not be performed on the subsequent day.

The plasma concentration data for memantine, provided by York Bioanalytical Sciences, will be analysed by Quotient Clinical using Phoenix WinNonlin v6.3 or a more recent version (Certara USA, Inc., USA).

The following PK parameter estimates will be obtained, where possible and appropriate: Cmax, AUC(0-t), AUC(0-168) and AUC(0-inf).

Relative bioavailability (Frel) of the selected memantine hydrochloride MR prototype capsule in the fed state compared to the fasted state (if tested).

Additional PK parameters and/or comparisons may be calculated, which will be detailed in the Reporting and Analysis Plan (RAP).

#### **MRI and X-Ray Assessments:**

Analysis of MRI data will be performed on Days 2, 4, 7, 10 and 14 to inform if the stellate formulation is retained in the stomach. If complete gastric emptying (all stellate components) is not confirmed on Day 14, subjects will be asked to return for a follow-up MRI scan between Day 14 and Day 25 (allowing a minimum 10-day window before admission to Period 2) to confirm complete gastric emptying of the stellate components. If any MR prototype is still present in the stomach at this follow-up MRI scan, subjects will not progress to Period 2 and will be managed in accordance with best clinical practice.

X-ray imaging (up to 2 abdominal X-ray per subject during the study; 1 per treatment period) may be performed in the non-fasted state to confirm elimination of the elastomeric core of the memantine hydrochloride MR prototype formulation by Day 21.

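### The synopsis describes no masking of whoever makes the live MRI residency call; withholding the food state and the chosen prototype is a cheap, partial safeguard

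*Combined protocol and SAP*

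**What the plan says.** All references are to section 3, Synopsis, the only part of the protocol supplied for this point.

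- **Design** (Methodology): "This is a single centre, open-label, single dose, 5-period study in 24 healthy male and female subjects". On structure: "It is expected the study will be executed in 3 cohorts of 8 subjects, with each cohort participating in up to 2 study periods". On order: "Subjects will be dosed in a sequential manner, as appropriate". Cohort 3 may overlap Cohort 2.
- **Primary objective**: to assess the gastro-retentive properties of the prototypes by MRI. It names no comparison. The effect of food on retention is a secondary objective marked optional.
- **The call** (MRI and X-Ray Assessments) is described so: "Analysis of MRI data will be performed on Days 2, 4, 7, 10 and 14 to inform if the stellate formulation is retained". Retention here means gastric residency.
- **What the call triggers** (MRI scans): if MRI confirms that the formulation has left the stomach, small-intestine images may be taken the same day. Separately, "No further MRI scans will be performed on subsequent days if stomach residency is not confirmed". Under Pharmacokinetic Assessments, the Day 2 and Day 4 results also decide whether the optional extra samples are taken the next day.
- **How the result is used** (Methodology): a decision after each regimen sets the next prototype and food state. The rationale offered for re-dosing a formulation with food is that "dosing in the fed state can improve gastroretention of oral dosage forms".
- **Reporting** (Statistical Methodology): retention is summarised descriptively by regimen, as number and percentage on each scan day. Formal modelling is confined to PK parameters.

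The synopsis does not say who reads the scans, how many readers there are, what criteria they apply, or whether they know the formulation or food state.

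**The concern.** The main result of the study is a person's judgement that a polymer object is, or is not, in the stomach. Clear images leave little room for expectation; equivocal ones leave some. The synopsis allows for equivocal images without defining how to read them. One rule acts when absence is confirmed, the other when presence is not confirmed, and an unclear image meets only the second. Complete emptying is defined by reference to every component of the stellate, but retention is not separated from partial retention.

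A reader who knows that a period was dosed with food, in a plan that expects food to help, could lean towards calling an unclear image present. The same image from a fasted period could be called absent. That would matter most for the fed-versus-fasted view of retention and for the interim choices that rest on it.

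**Working it through.** **1. The plan's own figure.** 3 cohorts × 8 subjects = 24, which matches the stated total. There is no power calculation to reproduce; the plan says that none was made.

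**2. Weight of one call.** Inputs: 8 enrolled per cohort and at least 6 evaluable per regimen (Sample Size and Power). One changed call moves a regimen's percentage by 100/n points.

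| n | one call | two calls |
|---|---|---|
| 8 | 100/8 = 12.5 | 200/8 = 25.0 |
| 6 | 100/6 = 16.7 | 200/6 = 33.3 |

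This is the granularity of any yes/no measure at these sizes. It says how much one call counts, not how often calls are wrong.

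**3. Effect of stopping after an unconfirmed scan.** A present call leads to another scan, so a later image can show the error. An absent call does not. Let f be the chance that a scan of a truly retained formulation is called absent. The documents give no value, so 2%, 5% and 10% are assumed, with scans independent and unscanned later days counted as not retained (also not stated). After k scans the chance of misclassification is 1 − (1 − f)^k.

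| f | by Day 7 (k = 3) | by Day 14 (k = 5) |
|---|---|---|
| 2% | 1 − 0.98³ = 5.9% | 1 − 0.98⁵ = 9.6% |
| 5% | 1 − 0.95³ = 14.3% | 1 − 0.95⁵ = 22.6% |
| 10% | 1 − 0.90³ = 27.1% | 1 − 0.90⁵ = 41.0% |

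If f were 0% in one regimen and 5% in another, both truly fully retained, the expected apparent gap would be 14.3 points on Day 7 and 22.6 on Day 14. These figures illustrate sensitivity only.

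**4. What could be hidden from a live reader.** Set side by side, the synopsis provisions give:

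- *Formulation, Regimens A to D*: one regimen per cohort-period, so subject number and date identify the slot and may reveal the formulation.
- *Food state, Regimens B to F*: may be changed for B to E on emerging data, and F may be fasted or fed. The date does not show which was chosen.
- *Prototype, Regimens E and F*: may be new or previously dosed, again decided during the study.
- *Scan preparation*: overnight fast, carbohydrate drink and water before every scan, whatever the regimen, so it does not disclose the food state at dosing.
- *Real-time decisions*: scan stopping, same-day bowel images, extra PK samples and the sentinel review need the residency result. None needs the reader to know the food state or prototype.

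**The case against.** The strongest case against the point has five parts.

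- **Masking would fail.** With one regimen per cohort-period, the slot is visible from subject number and date. This stands for the formulation in Regimens A to D. It does not stand for food state in B to F or for the prototype in E and F, which are chosen adaptively.
- **The reader is unknown.** Scans are performed at a university site, but the synopsis does not say that the call is made there; the investigator or delegate and the sponsor's medical monitor use MRI images for the sentinel decision. This stands. Any instruction must attach to the person making the call, not to a site.
- **The consequence is modest.** The judgement is about a physical object, the study is declared exploratory, and MRI results are descriptive. This stands and sets the level of the point. A reader might infer that a primary comparison of regimens is biased, but the primary objective names no comparison and no MRI test is planned.
- **Direction.** Expecting food to help pushes a fed scan towards present, which later scans can correct. This stands, so the carry-forward figures apply to absent calls, for instance on unclear images from fasted periods. No expected direction is stated among the prototypes.
- **Cross-checks exist.** Small-intestine images, faecal retrieval and, for radiopaque formulations, X-ray can all bear on a call. This stands in part: all are optional, and X-ray addresses elimination by Day 21 rather than residency on Days 2 to 14.

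Finally, only the synopsis is available. Fuller imaging instructions may exist, so the point can only be that the synopsis describes no masking.

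**Conclusion.** The point holds as a minor, low-cost improvement. The residency call is live, open-label on the face of the synopsis, consequential for later scans and for the next regimen, and made in a plan that states what it expects of food. Expectation could influence equivocal calls, chiefly in the optional fed-versus-fasted view of retention, and one call is worth 12.5 to 16.7 points.

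Three stronger readings are tempting and are not supported:

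- *That bias occurred, or is likely to be of a given size.* The documents give no misread rate.
- *That masking costs nothing and would be complete.* The documents give no reader or cost information, and the slot structure limits what can be hidden.
- *That a wrong absent call on Day 2 necessarily fixes the result on Days 4, 7, 10 and 14.* It ends the scheduled scans, but the synopsis does not say how unscanned days are counted, and the optional checks might expose the error.

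The conclusion assumes that some images will be equivocal and that the person reading them can be kept apart from the interim choice of food state and prototype.

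**What to change.** Add to MRI and X-Ray Assessments, in words such as: *The person who makes the gastric retention call, at whichever site, will not be told the prandial state at dosing or the prototype selected, and will record the call before any discussion with the clinical unit or the sponsor.* Scan requests should omit both items. Real-time reading and the scan-stopping rule stay unchanged. Because masking acts before the call, it also covers scans that a wrong call would cancel, which a later re-read of stored images could not recover.

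The cost is a small change to the request form and the imaging instructions. No extra scan is needed, and no extra reader provided that the present one does not take part in the interim choice. The masking will be partial: the slot may reveal the formulation for Regimens A to D, and subjects know whether they ate before dosing. The clinical study report should say so.
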